## QUALITATIVE

### 3.1 Qualitative Research Aims

Receive provider and patient feedback on the application of wearable technology to post-discharge care to conduct a theory-driven evaluation of feasibility, usability, and effectiveness. We will address motivational and self-care issues at baseline, continuing and post-study from both providers and patients' viewpoints. 1) ascertain perceptions of telemonitoring and remote patient management of high-risk patients, of organization and effectiveness of care by providers using interviews and surveys; and 2) evaluate patient acceptance, perceptions of and satisfaction with wearable patches, with prompted requests for patient status information, and with escalation pathways for nurse navigators and physicians using interviews and survey tools.

### 3.2 Experimental Plan and Methods

We will assess remote monitoring combined with non-invasive wearable technology's potential by applying the Affective Adaptation of the Technology Acceptance Model (A/TAM). We describe the approach to providers and patients in detail below. We stress that these will be linked to care delivery processes and the measures described above in the quantitative section to realize the full potential of a mixed-methods approach.

#### I. Ascertain providers' perceptions of telemonitoring and remote patient management of high-risk patients, organization, and effectiveness of care using interviews and surveys.

**Provider induction (prior to patient enrolment):** Provider induction will include an in-depth review of the wearable device, remote management, and escalation pathway, followed by an interview informed by A/TAM to establish each provider's comfort level (i) with wearable technology and any experience of such a device (e.g., habitual use of wrist-worn activity monitoring), and (ii) with wearable technology as a means of monitoring a post-discharge patient's status, including (iii) anticipated challenges in technology-mediated interaction with patients; and finally (iv) identification of any knowledge gaps that may need to be filled through the induction process.

**Provider progress monitoring (throughout the trial period):** Providers' progress and experience of the program will be assessed through: (a) a survey including open-ended questions with each provider following the completion of the study, to evaluate the extent to which anticipated issues and challenges may be realized. (b) a partly randomized, recurring opportunity to respond to one question once at the point of interaction with the patient; based on a matrix of questions, patients and providers, a single multiple choice question appears as part of a best practice alert to ensure that it is seamlessly integrated; nevertheless, collectively, all questions, all providers and all patients will receive adequate coverage.

**Provider satisfaction (after the trial):** At the conclusion of the study, providers: (a) will be debriefed through a comprehensive semi-structured interview to assess (i) their subjective perception of the effectiveness of wearable-mediated, post-discharge care; and (ii) actual challenges encountered in the course of the program (e.g., frequency of interaction, patients' comprehension of instructions, perception of patients' adherence, including any socio-emotional issues that may be impinging); (b) will participate in a post-trial half-day event to network with patients and the research team towards an open-ended

evaluation of the joint experience and to elicit opinions and contributions towards a follow-up randomized clinical trial proposal, and (c) will be invited to contribute to one or more joint evaluative publications.

A timeline illustrating provider related study activities can be found in Figure 4.

[figure not shown]

Figure 4 Provider Interview Timeline

II. To evaluate patients' acceptance, perceptions of and satisfaction with wearable patches, with prompted requests for patient status information, and with escalation pathways for nurse navigators, midlevel providers and specialists.

**Patient enrollment (prior to discharge):** Following a detailed presentation of the device and study, and informed consent, researchers will administer a questionnaire to establish the participant's comfort and experience level with a wearable device and to ascertain that the participant has understood the limitations of the devices (e.g. that they provide continual but not constant, "real-time" monitoring) prior to hospital discharge. This will be followed by an in-person semi-structured interview. The interview is informed by A/TAM to establish the patient's readiness to use a wearable device as a means of monitoring their post-discharge status, including to establish any anticipated challenges in technology-mediated interaction with the care team; and finally, to identify any knowledge gaps that may need to be filled through the induction process. Paradata will be collected at the interview to assist with analysis.

**Patient progress (throughout the period of device use):** Monitoring of the patient's experience and satisfaction with the device and the study process will be combined with weekly monitoring questions focusing on the following aspects: **(a)** experience with physical use and tolerance of the device; assess any difficulty in keeping it in place, any skin reaction, possible somatization of health concerns; **(b)** experience of self-monitoring and communication with care team through the device **(c)** degree of reassurance or anxiety about the patient's recovery process; finally, **(e)** paradata from device and interaction metrics, including possible sentiment analysis of interaction text.

[figure not shown]
**Conclusion (Study endpoint):** **(a)** Surveys will be administered at study endpoint to assess each patient's strength of feeling in each response by recording not only the response itself but also the "paradata"—the researcher's assessment of the patient's affect in providing the response. On this basis, **(b)** in

conjunction with process measures captured through surveys, the first patient group participants will complete a post-study interview with the researcher. Using a mixed methods philosophy, the interview will seek links between performance measures and the experience of participants. **(c)** The interview will link to the quantitative results in terms of outcome and process measures, as well as to the patient status reports throughout the 30-day period to propose hypotheses for further study, e.g. on subjective tolerability of the wearable device or faith in a remote monitoring system and care process measures, such as unscheduled visits. **(d)** Patients will be invited to a post-trial half day event to network with their providers and the research team towards an open-ended evaluation of the joint experience and to elicit opinions and contributions towards a follow-up randomized clinical trial proposal; and **(e)** will be invited to contribute to a publication on the patient experience and to review scientific publications by the research team.

For the ileostomy cohort, we will use think-aloud methods to compliment the semi-structured interviews during the study end-point interview. Patients will think-aloud and convey their thoughts and experience to interviewer while using the patch, phone, and physIQ app. The other topics during study end-point will continue with the semi-structured formats.

A timeline illustrating patient related study activities can be found in Figure 5.

*Figure 5 Patient Interview Timeline*

### 3.3 Content and focus of interviews

#### 3.3.1 Patient

Interview questions are developed based on A/TAM to elicit information. An example of the potential survey and interview questions the research team will use during the interview can be found in the appendices as **Appendix 1**.

**Table 8. Patient A/TAM Structure**

	Positive Affect	Negative Affect	Perceived Usefulness	Perceived Ease of Use	Attitude Toward Using	Behavioral Intention to Use	Actual System Use
Wearable Device	Past positive experience with using wearable devices	Past negative experience with using wearable devices (Technology anxiety)	Perceived usefulness of the wearable technology improving life quality/med adherence/ health management / health outcomes...  Perceived benefits/barr iers associated with wearable device	Perceived ubiquity of the wearable technology  Easiness of wearing/cha nging the patch  Easiness of using the mobile phone  Easiness of answering the survey via mobile platform	Positive attitude towards using the wearable device/mobile phone/techn ology  Negative attitude towards using the wearable device/mobile phone/techn ology	Compliant with device usage  Non-compliant with device usage	Readmission
Telemonitoring	Past positive experience with remote monitoring	Past negative experience with remote monitoring	Perceived usefulness of the telemonitoring process improving life quality/med adherence/ health management / health outcomes..	Perceived easiness of communicati ng with care team  Perceived easiness of following care team instructions	Positive attitude towards telemonitoring  Negative attitude towards telemonitoring	Compliant with clinical instructions  Non-compliant with clinical instructions	Readmission

			Perceived benefits/barrings associated with telemonitoring process				
Sociocultural factors	Positive disease management experience  Language (English)  Social support (Family/friend/PCP)  Marital status (Married, good support system)  Non-smoker  Good control over diet  Income status (Stable)  Traditional/R eligion values  Good mental health status	Negative disease management experience  Language (Non-English)  Social support (Family/friend/PCP)  Marital status (Single, Widowed, no support)  Smoking Hx  Poor control over diet  Income status (Unstable)  Traditional/R eligion values  Depression		Perceived control over the external factors	Self-motivation to tech usage adherence	Positive/Negative attitude towards technology and device acceptance	Self-care

**Demographic Form** – Sociodemographic information will cover gender, ethnicity, race, household income, education level and marital status.

**The Self-Care Self-Efficacy Scale** – The Self-Care Self-Efficacy Scale is authored by [name]. Confidence is not part of self-care per se, but a factor that greatly influences self-care. For this reason, [name] include a confidence (or self-efficacy) scale as part of the self-care scales. The Self-Care Confidence scale can be used alone.

**Stoma Quality of Life Scale** – The QOL instrument is a 21-item questionnaire that measures work/social function, sexuality/body image, and stoma function.

**Device User Experience** – These questions ask about patient's experience on using the vital patch and physIQ platform.

**Telemonitoring Experience** – These questions ask about patient's experience the telemonitoring process.

### 3.3.2 Provider

The survey and interview questions for the provider cohort are developed based on A/TAM to elicit information. An example of the potential survey and interview questions the research team will use during the interview can be found in the appendices as **Appendix 2**.

**Table 8. Provider A/TAM structure**

	Positive Affect	Negative Affect	Perceived Usefulness	Perceived Ease of Use	Attitude Toward Using	Behavioral Intention to Use	Actual System Use
Wearable Device	Past positive experience with using wearable devices with patients	Past negative experience with using wearable devices (Technology anxiety)	Perceived usefulness of monitoring patient vitals	Easiness of using the physIQ portal to review vitals  Easiness of using smart note template in EPIC	Positive attitude towards promoting the device for patient usage  Negative attitude towards promoting the device for patient usage	Intend to promote usage among patients	Engagement in device monitoring
Telemonitoring	Past positive experience with remote	Past negative experience with remote	Perceived usefulness of monitoring patient	Easiness of communication between	Positive attitude towards telemonitoring	Intend to practice telemonitoring as a method	Engagement in patient remote monitoring process

	patient monitoring	patient monitoring	disease progress	n providers Easiness of communication between patients Easiness of managing patient medication Easiness of providing clinical instructions	Negative attitude towards telemonitoring	for patient management	
Sociocultural factors	Individual's tendency to innovate in daily life  Individual's level of technology usage in personal life  Organizational level factors	Individual's tendency to innovate in daily life  Individual's level of technology usage in personal life  Organization al level factors	Will the usage of technology enable providers to reduce effort/enable patients to better disease manage	Organization support (education on device/tech usage)	Positive/Negative attitude towards participating in the program	Intention to participate in the program	Activeness in the program

**Demographic Form** – Demographic form will cover position title and the target patient population they are caring for.

**Device User Experience** – These questions ask about providers’ experience on using the physIQ platform. We developed this questionnaire based on the systematic usability scale (SUS).

**Telemonitoring User Experience** – These questions ask about providers’ experience in the telemonitoring process.

### 3.4 Interview methods

Semi-structured individual interviews will be used to maximize depth of detail and minimize bias introduced with cross-contamination from other interviewees. Researchers trained in semi-structured interview techniques will conduct the interviews. They will use a nondirective interview style, with open-ended questions, and allow the participant to adopt their own pace and style of response, along with freedom of subject matter, so that they may change and emphasize alternate points to those already brought up by the interviewer. We will use probes and follow-up questions when indicated, and new constructs and ideas will be allowed to emerge. The interviewer may take notes during interviews, but de-identified transcriptions will be the primary source for analysis.

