### 8.6.2 Ileostomy Study Endpoint Interview

Example of questions	Example of probing questions
Device	
Tell me about your experience using the device.	How was the patch/phone/physIQ app? Tell me more about that.

Home Health	Home health nurses are the nurses from Home Health that visits you at your house.
Tell me about your experience working with the monitoring nurse.	Were there any challenges?  Please tell me more about that.
Do you think the monitoring nurse have good awareness of your needs?	Why or why not?
In what ways, if any, did working closely with the monitoring nurse impact your health?	Why or Why not?
Care Team	Clinical Care Team are the physicians, physician assistants, nurse practitioners and nurses who took care of you during hospitalization.
Did your surgery team contact you, or did you contact your surgery team during the 30 day remote monitoring period?	Yes → Complete Care team question session  No → Skip entire Care team session
Tell me about your experience working with the clinical care team (for the past 30 days)	Were there any challenges?  Please tell me more about that.
In what ways, if any, did working closely with the clinical team impact your health?	Why or Why not?
Stoma	
Can you describe how daily life is now with the stoma?	How does the change impact your social life?  How does the change impact your work? (if applicable)

How would you compare your experience now with life prior to the colorectal surgery?	
Program	By program, we mean the whole experience wearing the devices, interacting with home health, and clinical care team.
What was it like to be part of this program?	
How practical do you think the program is?	
Were the instructions easy to follow?
 
Were the daily requirements easy to complete?
 
Why or why not?

What do you think about the discharge care you received for the past month?	
Do you feel like this study prevented a hospital readmission?  (Skip if patient is readmitted)	Why or why not?
Please walk me through how you (or your caregiver) managed your ostomy while enrolled in the program?	Tell me more about that.

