Has being in this program led to any changes in how you feel about your ostomy?	
What kind of changes? Tell me more about that.
 
Do you feel stressed about having an ostomy?
 
Did the study help you reduce stress for the past month? Why or why not?
 
Do you feel down or depressed about having an ostomy?
 
Did the study help you reduce depressing feelings for the past month? Why or why not?

Has the study made you feel more secure in the past month?	Why or why not?
Has the study empowered you to own and manage your care?	Why or why not? Or How/In what ways did it...
Were your family or friends assisting you with the devices?	
How does your family/friends feel about the program?
 
Do they feel like the program is practical? Why or why not?
 
Does it help ease burden of care? Why or why not?
 
Do you think you could have done the study without their assistance?

Please walk me through your feelings towards using the devices in the past month.
 
(Ex. Enthusiastic in the beginning → felt bored later or worried at the beginning → felt comfortable later)
	
I want to ask you a question for you to help us. How do you think we could make this program better?	
Is there anything you would like to add?	

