#### *Interview at Study Start Point*

Example of questions	Example of probing questions
What experience do you have with telemonitoring?	Yes → Tell me more about that  No → No probe  Vague response → Probe to see if they have telemonitoring experience (Experience during COVID-19 pandemic)
When you first heard about the program, what did you think about it?	What do you think about the workflow/protocol?  What do you think about the monitoring platform?
In what ways, if any, do you think the program could be beneficial to your patients?	Why or why not?
What expectations, if any, do you have about this program as this relates to your work?	

What supports do you think you will need, if any, with implementing remote monitoring?	What do you think it will take for us to continue offering this as standard of care?

For clinical team: How do you feel about implementing patient remote monitoring with Home Health?
 
For home health: How do you feel about implementing patient remote monitoring with the regular care team?
	Why or why not?
What concerns do you have about this program, if any?	
Yes → Tell me more about that
 
No → No probe
 
Vague response → Probe

Is there anything you think we should have asked you and didn't?	
For colorectal providers:	
What are your experiences with taking care of colorectal patients?	
What about new ileostomy patients?
 
Can you walk me through taking care of a typical ileostomy patient after discharge?
 
What were some challenges with patient care?
 
How do you think this study would help with patient care?

Sometimes patients have difficulty with treatment plan adherence and as a result they adapt based on their life situations.	
What do you think about this?
 
Is this frequent in ileostomy patients?
 
What tactics do you use to assist with adherence?
 
How effective do you think they are?

What are your thoughts on the study helping with patient communication?	Do you expect the communication to be more targeted and efficient?
What are your thoughts on the study helping patients (and or patient family) transition to this new life?	

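### Section 3.4 promises nondirective, open-ended interviewing, but several example items in the interview guides are closed or presuppose benefit and may tilt perceived-benefit themes toward the program

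*Protocol*

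**What the plan says.** Section 3.4 describes how the interviews are to be run: "They will use a nondirective interview style, with open-ended questions". Participants set their own pace and choice of subject, "so that they may change and emphasize alternate points to those already brought up by the interviewer". The section adds: "We will use probes and follow-up questions when indicated, and new constructs and ideas will be allowed to emerge".

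Sections 3.3.1 and 3.3.2 introduce the patient and provider guides in the same words: "An example of the potential survey and interview questions the research team will use during the interview".

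The patient endpoint guide (8.6.2) includes the main question "Has the study empowered you to own and manage your care" and the probe "Did the study help you reduce stress for the past month". The provider start-point guide (9.1) includes the probe "How do you think this study would help with patient care". The endpoint guide also contains a neutral model: "In what ways, if any, did working closely with the monitoring nurse impact your health".

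**The concern.** A nondirective style exists so that the participant, not the question, sets the direction of the answer. A closed question that names a favourable effect does the reverse. It offers one direction, and agreeing is the easy and polite reply to a researcher from the program. Any resulting bias would run toward the program.

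Section 3.1 uses the interviews in an evaluation that includes effectiveness, acceptance and satisfaction. The affected items concern readmission, security, empowerment, stress, mood and family burden, which are the themes closest to perceived benefit. Section 3.2 says the interviews will also generate hypotheses for further study. If the wording produces part of a theme, that part is carried forward as though it were experience.

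**Working it through.** No arithmetic bears on the wording, and the protocol gives no figure to reproduce. The check sets section 3.4 against the two guides, item by item.

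**Patient endpoint guide (8.6.2).** By hand count it has 21 main questions.
- *Closed, naming a benefit of the study:* three main questions. They ask whether the study prevented a readmission, made the patient feel more secure, or empowered the patient.
- *Closed and favourably worded, about the nurse:* one main question, on whether the monitoring nurse had good awareness of the patient's needs.
- *Closed, naming a benefit, as probes:* three. They ask whether the study helped reduce stress, helped reduce depressing feelings, or eased the burden of care for family and friends.

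That gives 3 + 1 = 4 of 21 main questions, plus 3 probes, so 7 items. None of the seven offers the opposite direction in its own wording. All seven are followed by a request for reasons either way, but only after the closed question has been put.

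**Provider start-point guide (9.1).**
- *Closed, naming a benefit:* one probe, on whether communication is expected to be more targeted and efficient.
- *Open in form but assuming benefit:* three items. One is the probe "How do you think this study would help with patient care". The other two are main questions asking for thoughts on the study helping with communication and helping with the transition to life after surgery.

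That gives 1 + 3 = 4 items. Across the two guides, 7 + 4 = 11 items are closed or presuppose benefit.

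**Comparison with section 3.4.** The eight closed items (7 + 1) are not open-ended. The three presupposing items are open-ended but not nondirective. The permission to use probes when indicated does not cover the four main questions in 8.6.2, and it does not suspend the nondirective style for the probes.

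**Why the setting matters.** Section 2.2 plans 10 patients and no comparison group, so a tendency to agree cannot be set against the same tendency in another arm. Section 4.3.1 allows a consent form without interviews, so the number interviewed may be below 10. In so small a set, one or two prompted answers can shape a theme.

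**Size.** Section 3.6 plans thematic coding and no proportion of favourable answers. The protocol gives no rate at which patients agree with leading items. The size of any tilt therefore cannot be derived.

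**The case against.** The other side has several sound points.

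- The guides are offered as examples, and section 3.4 places the safeguard in the conduct of trained interviewers. This stands as mitigation. But these are the only guides in the protocol, they are described as questions the team will use, and 8.6.2 carries working skip instructions.
- Most main questions are open or neutral, and some invite criticism: challenges met, ways to improve the program, and providers' concerns.
- The stress and mood probes sit under a main question that asks, without direction, whether feelings about the ostomy changed. The burden probe follows an open one on how family and friends feel. The patient is therefore not met first with a benefit statement on those topics.
- Worry and family help are partly covered elsewhere. The endpoint guide asks about feelings toward the devices over time, giving worry as an example, and whether the patient could have managed without family. The Week 3 questions in 8.3 ask about self-consciousness of symptoms. The reassurance-or-anxiety target in section 3.2 belongs to the weekly questions and concerns recovery, so the endpoint interview does not breach it.
- Provider induction precedes patient enrolment, so the start-point items elicit expectations. They cannot overstate experienced benefit.
- The coding framework has constructs for negative affect and negative attitude, and surveys supplement the interviews.

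These points limit the concern. None of them makes the 11 items nondirective and open-ended. A request for reasons does not undo the direction of the question before it, and a framework with negative constructs can code only what was elicited.

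**Conclusion.** The contradiction is real but limited. Seven items in the endpoint guide and four in the start-point guide do not follow section 3.4, and their wording may tilt the perceived-benefit themes toward the program. This rests on the ordinary expectation that one-sided questions invite agreement, and on interviewers using the items roughly as printed.

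A reader might infer that the guides as a whole are leading, that perceived benefit will be overstated, or that an assumed agreement rate could be turned into a number of extra favourable answers. The protocol supports none of these. The affected items are a minority, most of the guide is neutral, and no count of favourable answers is planned. The finding is a risk of bias in a known direction and of unknown size. It touches the qualitative themes only, not any numerical estimate or decision rule. It deserves correction because the correction is simple.

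**What to change.** Reword the 11 items in the neutral form already in the guides. Suggested wordings:

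- *In what ways, if any, has the program affected your stress, your mood about the ostomy, how secure you feel, or how you manage your care, for better or worse?* (asked topic by topic)
- *In what ways, if any, did the program affect your need to return to hospital, for better or worse?*
- *How well did the monitoring nurse understand your needs?*
- *In what ways, if any, did the program change the work for your family?*
- For providers: *In what ways, if any, do you expect the study to affect patient care and communication?* A parallel item can cover patients' transition to life after surgery.

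Tag each transcript with the guide version, so that old and new wordings are not merged unnoticed on these themes. Amending section 3.4 to admit directed questions would remove the contradiction but leave the possible tilt, so rewording is preferable.

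The cost is an edit to Appendices 1 and 2, with no added visits, interview time or participants. The one small downside is that interviews already held under the old wording are not directly comparable on these themes and should be reported as such.
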